3. Study Design

This study is a single-center, prospective, non-blind, parallel-group, randomized controlled trial with an active comparator.

4. System technical specifications

The version of SWORD Phoenix used in this study is composed of the following components:

- a) **Inertial motion trackers:** each one is composed of a three-axis gyroscope, three-axis accelerometer and a three-axis magnetometer, allowing 3D

Version 2.0

Date: 06/14/2018

movement analysis and quantification. The trackers communicate via Bluetooth LE with a tablet computer.

- b) **Mobile App:** a mobile app that processes the information generated by the motion trackers and provides real-time biofeedback regarding movement quality and patient performance.
- c) **Web-based Portal:** a web-based platform that allows the clinical team to prescribe motor tasks and monitor results.

Motion Trackers

The motion trackers are placed on body segments using Velcro® straps. Each motion tracker is placed in a specific position. To assist in the correct placement of the motion trackers, both the trackers and the matching straps are color-coded. In this study, the following setup will be used:

- **Red tracker:** over the sternal manubrium
- **Green tracker:** on the medium third of the external surface of the upper arm, pointing to the elbow
- **Blue tracker:** on the dorsal surface of the distal third of the forearm, pointing to the hand

Mobile App

The mobile app guides the patient in each exercise session. Before each exercise, the

patient is presented with a real-life video and audio explanation of that exercise. The execution interface is subsequently shown. This screen features: a) a posture dummy indicating correct/incorrect posture; b) a progress bar; c) a timer indicating rest time between repetitions and prompting start when rest time is over; d) a repetition counter; e) a star counter and f) a timer displaying time left to complete the exercise.

Only correctly performed repetitions count towards the repetition counter. A correct repetition is defined as a movement starting at the baseline and reaching or surpassing the specified target, without violating movement or posture constraints. In case the patient violates a movement constraint, a message is prompted showing which movement error was performed, so that the patient can correct the movement in the following attempts.

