- i) Major medical complications occurring after surgery that prevent the discharge of the patient within 5 days after surgery
- j) Other medical and/or surgical complications that prevent the patient from complying with a rehabilitation program
- k) Blind and/or illiterate patients

10. Methods for identifying and recruiting patients

All patients admitted for rotator cuff repair during the study period will be screened for inclusion and exclusion criteria.

When a potential candidate is identified, the local investigator will approach the candidate and explain the study in detail. The prospective candidate will be given the patient information document and sufficient time to consider whether he wishes to participate in the study.

Subsequently, the prospective candidate will be given opportunity to clarify any

doubts, after which the informed consent form will be signed and dated in duplicate by the patient and the investigator. Only then will the randomization and baseline assessments be performed.

11. Patient allocation to study groups

For logistic reasons, the study will be restricted to patients living in a 20km radius around the investigation center. Patient allocation to the two groups will be performed in a random way, in a 1:1 ratio in blocks of six. This will be done using an online randomizer (<https://www.randomizer.org>).

The allocation of patients to each group will be performed centrally by one investigator - [name] - and communicated to the responsible for data acquisition only after patient enrollment. This investigator will not be involved in data collection or in outcomes assessment.

12. Blinding

The nature of the study does not allow blinding of the patients regarding study groups. However, participants will be blinded to the primary and secondary outcomes being measured. All patient assessments will be performed by an investigator blinded for randomization groups. Statistical analysis will be performed blinded for randomization group.

13. Patient assessment

Patients will be assessed pre-operatively, and then at 6, 12, 16 and 20 weeks after the surgery. In patients where a decision is made to extend the program to 24 weeks,

another assessment will be made at this point. An assessment will also be made at 12 months after surgery.

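### Fixed blocks of six, printed in the protocol, could let a recruiter who learns earlier allocations foresee up to a quarter of them, and the plan does not say the recruiter is kept unaware

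*Combined protocol and SAP*

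**What the plan says.** Section 3 describes a "single-center, prospective, non-blind, parallel-group, randomized controlled trial". Section 11 sets allocation "in a 1:1 ratio in blocks of six" and adds: "This will be done using an online randomizer". It gives no second block size, mentions no stratification factor, and does not withhold the block size from site staff.

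The safeguards are these. One investigator allocates centrally, and the result is "communicated to the responsible for data acquisition only after patient enrollment". Of the allocator, section 11 says: "This investigator will not be involved in data collection or in outcomes assessment". Section 10 places consent ahead of allocation: "Only then will the randomization and baseline assessments be performed". Section 12 blinds the outcome assessments and the statistical analysis.

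On recruitment, section 10 says that "the local investigator will approach the candidate and explain the study in detail". On patients, section 12 says: "The nature of the study does not allow blinding of the patients regarding study groups". No section says whether the recruiting investigator learns the arms of earlier patients, or whether the recruiter is the person responsible for data acquisition to whom section 11 sends the allocation.

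**The concern.** Central holding of the list conceals the next assignment only if it cannot be worked out. In a 3+3 block of known size, once three patients have gone to one arm, the rest of that block must go to the other. With one centre, one sequence and a fixed size, block starts follow from counting enrolments: patients 1, 7, 13 and so on.

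Foreknowledge before consent allows selective enrolment. Several entry criteria in sections 8 and 9 call for judgement, such as whether a tear is reparable, whether the patient can follow motor commands, and whether comorbidity would interfere with compliance. A candidate could be deferred or discouraged according to the arm that is due. Blinded assessment cannot undo this, because the selection happens before randomisation. The section 16 comparison, a t test or Mann-Whitney test on change in a per-protocol set, includes no covariate adjustment that might soften it. With about 34 patients per arm, a few selectively placed patients could shift prognosis between groups.

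**Working it through.** **Inputs.** Block size 6, ratio 1:1 (section 11). One centre (section 3), no strata stated, so one running sequence. Total of 68 patients (section 6).

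**The plan's own figure.** The plan gives no predictability figure. Its only relevant number is 68, which sets the number of blocks. That total can be reached: 2 × (1.960 + 1.282)² × 12.0² / 10.4² gives 28 per arm; dividing by the Mann-Whitney efficiency 3/π gives 30; dividing by 0.9 for dropout gives 34 per arm, or 68. The plan does not say it used this route, and the shares per block below do not depend on it.

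**Certain allocations, fixed blocks of six.** There are 20 equally likely arrangements of three and three. A position is determined when one arm is already used up.

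- Position 4 is determined if the first three are alike: 2/20 = 10%.
- Position 5 is determined if three of the first four are alike: 8/20 = 40%.
- Position 6 is always determined.

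If the latest allocation has not yet reached the recruiter, each figure moves one position later; if the latest two have not, it moves two.

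| Position | All earlier known | Latest unknown | Latest two unknown |
|---|---|---|---|
| 1 to 3 | 0 | 0 | 0 |
| 4 | 10% | 0 | 0 |
| 5 | 40% | 10% | 0 |
| 6 | 100% | 40% | 10% |
| Expected per block | 1.5 | 0.5 | 0.1 |
| Share of 6 | 25.0% | 8.3% | 1.7% |

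The closed form for a block of 2m with full knowledge is 2m/(m+1); with m = 3 it is 6/4 = 1.5, which agrees. If the latest three are unknown, the share is zero.

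**Over 68 patients.** 68 = 11 full blocks + 2 patients, and the last two add nothing. With full knowledge, 11 × 1.5 = 16.5 patients (24.3%). With a lag of one, 11 × 0.5 = 5.5 patients. With a lag of two, 11 × 0.1 = 1.1 patients.

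**Best guess, full knowledge.** The chance of guessing correctly by position is 0.5, 0.6, 0.6, 0.7, 0.7 and 1.0. The sum is 4.1, and 4.1/6 = 68.3%, against 50% by chance. Over 68 patients it is (11 × 4.1 + 0.5 + 0.6)/68 = 67.9%.

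**Randomly varied blocks.** Simulation of 68 patients (4,000 runs), with a guesser who knows every earlier allocation and the set of possible sizes but not the order in which they are used:

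- Sizes 4, 6 and 8: 2.2% certain (about 1.5 patients), best guess 67.8%.
- Sizes 4 and 6: 5.6% certain, best guess 69.1%.
- Sizes 2, 4 and 6: 4.1% certain, best guess 70.1%.

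**The case against.** The strongest reply is that 25% needs a recruiter who knows every earlier arm in the block without delay, and nothing in the documents says so. Allocation is central, follows consent, and goes to one named role. Treatment takes place at home and starts two weeks after surgery (section 14), so it is not on view at the hospital when the next candidate is approached. Seeing the device does not reveal the arm either, because it measures range of motion in all patients (section 13.1.3). If the recruiter is also the blinded assessor, which the text allows, the share is zero. All of this stands as a limit on size. A reader might infer that the recruiter will know a quarter of allocations in advance; the documents support only a possible maximum.

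A reader might also take the trial as wholly unmasked from the design label in section 3. Section 12 contradicts that for assessors and analysis. Nor do the documents show that the recruiter personally makes the entry judgements: all patients admitted for repair are screened, tears need imaging evidence, and the indication comes from the patient's surgeon.

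Two further points stand. Varying the sizes hardly changes the success of a good guess. And with a lag of two, fixed blocks already give only 1.7% certainty. The second point does not dispose of the concern, because the plan gives neither an accrual rate nor a rule on who learns allocations, so no lag can be relied on. Patients know their arm, and the surgeon, who sets the indication, also decides on programme extension and is told of detrimental progression, so routes to this knowledge exist.

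**Conclusion.** The point holds as a conditional one. With the stated fixed block of six, between 0 and 25% of allocations (0 to about 16 or 17 of 68) are foreseeable with certainty, depending on what the recruiter learns and when. The upper end assumes knowledge of all earlier allocations and of the block starts, and a list used in strict order without strata. The plan does not say that the recruiter is kept unaware, and it prints the one fact needed for the deduction.

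This is a cheap improvement worth making. It is not evidence that concealment has failed, and permuted blocks with central allocation are not in themselves an error. What is gained is the removal of certainty, from at most a quarter to about 2%; it would be wrong to claim that the sequence becomes unguessable.

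**What to change.** In section 11, replace the fixed block with randomly varying block sizes. The sizes 4, 6 and 8 serve here as an example; the sizes actually used should be held only by the central allocator and kept out of any document that recruiting staff read. If enrolment has begun, which the documents do not show, apply this to the unused remainder of the list, starting at the end of the current block.

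Also state in sections 10 to 12 that those who approach, screen and consent candidates do not see earlier allocations, and say whether the person responsible for data acquisition is separate from the recruiter and from the blinded assessor. This statement matters most, because it also limits guessing, which varied blocks do not.

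The cost is a new list, a minor amendment to a protocol that already has ethics approval (section 19), and slightly more possible imbalance from an incomplete last block. That imbalance can reach half the block size: 4 with a block of eight, against 3 with a block of six, or 2 if recruitment stops at exactly 68.

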13.1 Baseline assessment

Participant characterization will consist of:

- a) Demographics (gender, date of birth);
- b) Educational level (years);
- c) Affected side
- d) Injured structures
- e) Size of tear
- f) Date of surgery
- g) Comorbidities
 - a. Factors affecting tissue healing: Smoking, Diabetes, Steroid intake
 - b. Other disorders: cardiac, respiratory, hypertension
 - c. Time between diagnosis and surgery
- h) Body Mass Index
- i) Constant score
- j) QuickDASH
- k) Shoulder range of motion

13.1.1 Constant Score

The Constant Score is a functional assessment score specific to the shoulder region, that varies between 0 and 100 points, being 100 the best score possible. This total score is distributed in subjective assessments of pain and activities of

daily living (15 and 20 points, respectively) and objective measures of shoulder range of motion and strength (40 and 65 points, respectively).⁵⁵

The Constant Score is the most used instrument to assess the shoulder in Europe and its psychometric properties prove it to be a valid, reliable and responsive measure.^{56,57} Kukkonen et al. (2013)⁵⁶ determined that the Minimum Clinical Important Difference - MCID of the Constant Score for patients with arthroscopically treated rotator cuff repairs was of 10.4 points.

13.1.2. QuickDASH

The shortened version of the Disabilities of the Arm, Shoulder and Hand (QuickDASH) is an 11-item self-administered outcome measure, specific to measure disability and symptoms in individuals with musculoskeletal disorders of the upper limb.⁵⁸ Each item has a 5 option Likert scale, from “no difficulty” to “unable to do” (1 to 5), and the total raw score is obtained through the sum of the answers and then converted into a 0-100 scale with a negative orientation, in which no disability indicates a score of zero and maximum disability a score of 100, determining the functional activity level. It is an instrument widely used for clinical or research purposes and which has proven to be a valid, reliable and responsive measure.^{54,58,59} Franchioni et al. (2014)⁵⁹ have determined the MCID for the QuickDash in patients with study pain as 15.19.

13.1.3 Shoulder range of motion

The shoulder range of motion will be measured in the sitting position.

The system used in the study is a validated medical device for joint angle measurement. Therefore, shoulder range of motion will be measured automatically

SH-RCT-ARCR-01 Study Protocol

by the system.

In this study, active range of motion will be measured in the following movements:

- a) Elevation of the shoulder in the scapular plane, sitting: with the patient sitting, with the arm fully extended, have the patient actively raise the arm in the scapular plane as much as possible, with extended elbow.
- b) Sitting shoulder flexion: with the patient sitting, with the arm fully extended, have the patient actively raise the arm as much as possible, with extended elbow.
- c) Sitting Shoulder Abduction: with the patient sitting, with the arm as close as possible to the body, have the patient actively open the arm as much as possible, with extended elbow.
- d) Sitting Shoulder External Rotation: with the patient sitting with 90° bent elbow and hand pointing forward, have the patient actively rotate the arm outwards, as much as possible.

In order to achieve this, the investigator will need to:

- 1) Create a new patient in the Phoenix Portal
- 2) Prescribe these four different exercises, described above
- 3) Setup SWORD Phoenix
- 4) Ask the patient to perform five repetitions of each movement to the best of his ability, while SWORD Phoenix records movement parameters
- 5) After the session, login to the Portal, go to the session's results and click on detailed results for each exercise. Record the value of best repetition for each exercise in the patient file.

13.2 Assessments at 6, 12, 16, 20 (and/or 24) weeks after surgery and assessment

12 months after surgery

These assessments will include:

- a) Constant score
- b) QuickDASH
- c) Shoulder range of motion (as described for the baseline assessment)

14. Intervention

Both study groups will receive early-onset home-based rehabilitation for 20 weeks, starting two weeks after surgery.²⁸ This program can be extended for another 4 weeks if necessary.

The experimental group will perform daily home-based rehabilitation sessions using SWORD Phoenix, under remote monitoring by a physiotherapist, as well as home one-to-one physiotherapy sessions, with decreasing periodicity depending on program stage.

The conventional rehabilitation group will receive home-based rehabilitation provided by a physiotherapist, 3 times a week, for 1 hour. Patients will also be instructed to perform additional unsupervised sessions in at least two other days of the week. Compliance to these additional sessions is not mandatory, but patients will be asked to fill in a diary regarding these extra-sessions.

The intervention arm, additionally to the one-to-one sessions, will perform daily home-based rehabilitation sessions using the system alone, under remote monitoring

SH-RCT-ARCR-01 Study Protocol

by a physiotherapist. Patients will be instructed to perform exercise sessions at least 5 times per week, but compliance to that frequency is not mandatory per protocol. The number of sessions, daily adherence and total training time will be registered automatically by the system and will be made available through the Web Portal, from where it can be transcribed to each patient file. When required, additional visits or telephone calls for technical assistance can be performed by the physical therapist. These will be registered as such in the patient file.

In the absence of a gold standard, the rehabilitation protocols were designed taking into account: a) a recent systematic review on the subject;⁴ b) a review of the concepts and evidence-based guidelines on this subject by van der Meijden *et al.* (2012)¹⁵; c) an overview of systematic reviews comparing early and conservative rehabilitation²⁸ and d) the protocol of the Massachusetts General Hospital for rehabilitation after rotator cuff repair.

The rehabilitation program will be based on the principles outlined in the following tables 1-4. In any case, these protocols can be tailored to the patient's specific needs, according to the assessment of the orthopedic surgeon and the physical therapist.

Table 1. Immediate Post-op Phase

Rotator cuff repair program: Immediate Post-op Phase (weeks 0 to 2) - Immobilization period	
Goals	Precautions
Control pain and swelling	
Protect the rotator cuff repair	Do not lift the operated arm
Protect wound healing	
Prevent shoulder stiffness	
Intervention	
Conventional PT group	Experimental Group
Use of a sling during the day and during the night until week 4	
Ice pack application to the operated shoulder for 15 minutes if necessary to reduce pain and swelling several times per day	
Promote the active movement of fingers, hand and elbow to increase circulation	
Gentle pendulum exercises for three to five minutes every one to two hours	

Table 2. Phase 1 of the rehabilitation program (weeks 2 to 4)

Rotator cuff repair program: Phase 1 - Immobilization period	
Goals	Precautions
Control pain and swelling	
Protect the rotator cuff repair	Do not lift the operated arm
Protect wound healing	
Prevent shoulder stiffness	
Intervention	
Conventional PT group 2 weeks 2 face-to-face sessions per week	Experimental Group 2 weeks: 1 face-to-face session per week Daily sessions with SWORD Phoenix
Ice pack application on the shoulder for 15 minutes to reduce pain and swelling	Intervention of the Control Group + SWORD Phoenix Exercises: - Scapula Elevation - Scapula Protraction - Scapula Retraction - Elbow Flexion - Forearm Supination - Forearm Pronation - Pendular Exercises
Active mobilization exercises of the scapula, elbow, forearm and hand	
Pendular exercises	
Drainage massage, when needed	

Table 3. Phase 2 of the rehabilitation program (weeks 5 to 7/9)

Rotator cuff repair program: Phase 2 - passive mobilization	
Goals	Precautions
Maintain integrity of the repair Avoid overstress healing tissue Gradually increase soft passive range of motion Diminish pain and inflammation Prevent muscular inhibition Begin early shoulder motion Reach 120° passive scapular mobility Reach 40° passive external rotation Reach 120° passive shoulder flexion	No active elevation for the first six weeks No lifting of objects No excessive stretching or sudden movements No supporting of body weight by hands Avoid resisted exercises and exercises in coronal plane abduction No mobilization of the shoulder for flexion on the scapular plane (20° to 30°) between 60° and 110° if rotator tear suture Avoid shoulder external rotation until the 8 th week if shoulder instability
Intervention	
Conventional PT group 5 weeks 3 face-to-face sessions/week	Experimental Group 5 weeks:2-2-2-1 face-to-face sessions* daily sessions with SWORD Phoenix
Ice pack application on the shoulder for 15 minutes to reduce pain and swelling Sub-maximal isometric strengthening: internal and external rotation at neutral Start soft passive ROM movements: - Limit lying internal rotation to 30° in the scapular plane (20° to 30°) - Lying external rotation to 60° in the scapular plane (20° to 30°) - Lying shoulder flexion in the scapular plane (20° to 30°) When passive ROM starts to improve, progress to soft active-assisted exercises (lying flexion, external and Internal rotation) Exercises: Ball squeezes, AROM for elbow, forearm and hand, scapular elevation and retraction	Intervention of the Control Group + SWORD Phoenix Exercises: - Scapula Elevation - Scapula Protraction - Scapula Retraction - Elbow Flexion - Forearm Supination - Forearm Pronation

Legend: * progressing to 1 session/week when possible

Patients may progress to the next phase after completing all passive range of motions of the shoulder described with no pain associated.

Table 4. Phase 3 of the rehabilitation program (weeks 8-10 to 12-14)

Rotator cuff repair program: Phase 3 - active movements	
Goals	Precautions
Maintain integrity of the repair and avoid overstress healing tissue Gradually increase to assisted and active range of motion Progressive scapular stability Progressive functional training Restore full shoulder motion	Respect previous precautions Do soft strengthening exercises under 1,5kg Weight training precautions Avoid excessive force on the shoulder
Intervention	
Conventional PT group 5 weeks 3 face-to-face sessions/week	Experimental Group 5 weeks: 1 face-to-face session/week daily sessions with SWORD Phoenix
Gradually progress to full ROM all planes: increasing angles of abduction in external and internal rotation and lying horizontal adduction Active-assisted arm flexion, progressing to active shoulder flexion Dynamic exercises: 
- Side-lying and sitting external rotation;- Side-lying and standing scaption- Prone row, T, extension and scaption- External Rotation- Wall Slide- Internal Rotation behind back- Horizontal Abduction Stretching: 
- Prone extension- Lying external Rotation/with abduction- Lying/standing/sitting active-assisted Arm Elevation- Standing forward flexion ("full can") exercise- Supine Cross-Chest Stretch- Wall slide Stretch	Intervention of the Control Group + SWORD Phoenix: 
- Scapula Elevation- Scapula Protraction- Scapula Retraction- Elbow Flexion- Forearm Supination- Forearm Pronation- Shoulder Flexion- Shoulder External Rotation- Shoulder Internal Rotation- Shoulder Horizontal Abduction- Arm circles with 90° flexion- Push-up against a wall

Patients may progress to the next phase after completing all active range of motions of the shoulder described with no pain associated.

Table 5. Phase 4 of the rehabilitation program (weeks 13-15 to 18-20)

Rotator cuff repair program: Phase 4 – strengthening	
Goals	Precautions
Maintain integrity of the repair and avoid overstress healing tissue Progressive rotator cuff strengthening and scapular stability Progressive functional training Re-establish dynamic shoulder stability Re-establish scapulohumeral rhythm Restore full shoulder strength Gradually begin to return to normal activity	Respect previous precautions Do soft strengthening exercises under 3,0kg Weight training precautions Avoid excessive force on the shoulder
Intervention	
Conventional PT group 6 weeks 3 face-to-face sessions/week	Experimental Group 6 weeks:1-0-1-0-1-0 face-to-face sessions daily sessions with SWORD Phoenix
Continue as above and progressively add: - Shoulder Abduction to full ROM Theraband exercises: - Standing external rotation (at 0° abduction) - Standing internal rotation (at 90°) - Standing shoulder flexion - Standing forward punch - Standing dynamic hug - Standing W's (external rotation with elbow flexion) - Standing Biceps curls - Seated row Dynamic strengthening exercises (first weeks limit resistance to max 1,5 to 2,5 kg): - Scapulohumeral rhythm exercises - Side-lying external rotation at 0° - Prone row, Scaption "Y", Extension - Standing forward flexion 1,5-2kg (scaption) - Standing external rotation at 90° abduction	Intervention of the Control Group + SWORD Phoenix exercises (adding Theraband or weight): - Scapula Elevation - Scapula Protraction - Scapula Retraction - Shoulder Flexion - Shoulder External Rotation - Shoulder Internal Rotation - Shoulder Abduction - Shoulder Horizontal Abduction - Seated Press-up - Push-up against a wall - Diagonals to flexion - Arm circles with 90° flexion - Arm circles with 90° abduction

Note: * may be less if patient is progressing well

The rehabilitation program may be extended until 24 weeks, according to the orthopaedic surgeon assessment.

Version 2.0

Date: 06/14/2018

Schedule of face-to-face sessions

The following schedule depicts the number of face-to-face sessions according to the “normal” protocol, not counting with the exceptions, ie, patient who can proceed to the following Phases earlier.

Table 4. Face-to-face session schedule

	Weeks	Conventional PT	Experimental
Immediate Post-op Phase	1	0	0
	2	0	0
Phase 1 - Immobilization Weeks 3 to 4	3	2	1
	4	2	1
Total Phase (accumulated)		4 Sessions (4)	2 Sessions (2)
Phase 2 - PROM Weeks 5 to 9	5	3	2
	6	3	2
	7	3	2
	8	3	2
	9	3	1
Total Phase (accumulated)		15 Sessions (19)	9 Sessions (11)
Phase 3 – AROM Weeks 10 to 14	10	3	1
	11	3	1
	12	3	1
	13	3	1
	14	3	1
Total Phase (accumulated)		15 Sessions (34)	5 Sessions (16)
Phase 4 – Strength Weeks 15 to 20	15	3	1
	16	3	0
	17	3	1
	18	3	0
	19	3	1
	20	3	0
Total Phase (accumulated)		18 Sessions (52)	3 Sessions (19)

15. Safety and adverse events

Patients in the active comparator group will receive face-to-face rehabilitation sessions provided by a physical therapist. Therefore, patient safety will be ensured at all times during the sessions. Patients will be able to report adverse events to their physical therapist. Moreover, the patient's orthopedic surgeon will be notified in case of detrimental clinical progression, so that the patient can be re-evaluated.

For patients in the experimental group, safety of the remote sessions will be evaluated through pain and fatigue scores (graduated from 0 to 10) collected at the end of each session. These will be presented to the patient using the mobile App and will be available for remote monitoring by their physical therapist. In case of excessive pain or fatigue, patients will be contacted by their physical therapist to ascertain the cause and change prescription if needed. Patients will also be asked to report any other adverse events to their physical therapist by telephone. Moreover, the patient's orthopedic surgeon will be notified in case of detrimental clinical progression, so that the patient can be re-evaluated.

The adverse events will be registered in the patient's file (beginning date, resolution date (if applicable), resolution state, severity).

16. Statistical analysis

To assess differences in clinical and demographic variables of the patients allocated to the two study groups, independent samples t test or Mann-Whitney U test will be used for quantitative variables. For qualitative variables, Chi-squared test or Fisher's exact test will be used.

Outcome analysis will be performed using a per-protocol analysis. The impact of the interventions in the primary and secondary outcomes will be evaluated considering

the change between baseline and week 20. Differences between the two study groups will be performed using independent samples t test or Mann-Whitney U test.

Since outcomes will be measured in several different times during the rehabilitation program, a repeated measures analysis will also be performed, using a 3x2 ANOVA with group as an independent factor and time as a within-subjects factor.

17. Potential Risks and Benefits to Participants

There are no invasive procedures involved in this research protocol and, given the nature of the intervention, no relevant risks are foreseen.

Both study groups will benefit from a 20-24 week rehabilitation program starting on week 2 after surgery. This program will be based on the latest treatment guidelines and will therefore represent the state of the art regarding rehabilitation after arthroscopic rotator cuff repairs. Thus, both study arms are likely to benefit directly from entering the study.

The experimental group will perform, in addition to the one-to-one physiotherapy sessions, a home-based program using SWORD Phoenix. This program will be tailored to their specific needs and be accompanied remotely by a physical therapist, that will have access to patient performance data, as well as pain and fatigue scores as rated by the patient at the end of each session. This allows the therapist to detect adverse events and to act promptly. In case of detrimental clinical progression, the patient's orthopedic surgeon will be notified, and the patient will be re-evaluated, to decide whether to continue the study. This ensures patients in the experimental group are not subject to greater risk.

Participants will not receive any payments or reimbursements specifically for taking part in this study.

18. Confidentiality of Personal Data

Data collection for this study was authorized by the National Commission on Data Protection, with the authorization number 5798/2018.

Personal data will only be accessible to authorized investigators in this study.

Personal data will not be entered into the database as part of this research. The clinical data collected will only be linked to the patient by a unique study number and will contain no personal identifiers. Informed consent will be obtained from participants to collect and retain this data. The data that will be used for analysis and dissemination for research purposes will be completely anonymized.

19. Ethical issues

All participants will be provided with information about the purpose and procedures of the study and will give written informed consent before inclusion.

The study was approved by the Ethics Committee of Hospital da Prelada (Authorization number 42-26/06/2018).

20. Dissemination of Results

The results of the study will be published in peer-reviewed scientific journal(s) and presented at relevant national and international meetings.

References

